After treatment, no special care is usually necessary for the treatment site. Aquaphor (similar to Vaseline) may be supplied to the subject to be applied to any area that feels irritated. The subject will also be instructed to apply cool compresses if they have any areas of swelling after treatment and to wash the treated area with soap or a gentle cleanser as they normally would for the week following treatment. The subject will be able to continue with their preferred routine skin care, excluding any method of wrinkle removal, the day after treatment. Sunscreen should be worn.

Data Recording

All data will be recorded in source documents and transcribed onto Case Report Forms (CRFs). Site will be monitored by Syneron staff or designees to assure adherence to the clinical trial requirements, subject safety, protocol procedures, and for data accuracy. The Case Report Forms and images will be reviewed and retrieved during the monitoring visit. All source documentation will remain in the subject's files at the site.

Protocol Revisions and/or Deviations

With the exception of emergency situations, no changes or deviations in the conduct of this protocol will be permitted without the prior approval of the sponsor.

The IRB/IEC that granted original approval for the study must be notified of all changes in the protocol and will approve any change or deviation that may increase risk to the subject, and/or that may adversely affect the rights of the subject or validity of the investigation.

 Candela Corporation Confidential	Pilot Study to Evaluate Combined Vbeam[®] Pulsed Dye Laser Treatment and RHOFADE[™] (oxymetazoline hydrochloride) Topical Cream for Erythematotelangiectatic Rosacea			
	Protocol #	DHF24671	Rev. Date	June 11, 2018

In the event of an emergency, the Investigator will institute any medical procedures deemed appropriate. However, all such procedures must be promptly reported to the sponsor and the IRB/IEC.

ADVERSE EVENTS (AE)

An adverse event (AE) is any adverse change in health or side effect that occurs in a study participant during their participation in the study.

Anticipated Adverse Effects

Anticipated adverse effects of laser-based treatments include: hyperpigmentation, blistering, crusting, bruising, scabbing, scarring, hypopigmentation, infection, and pinpoint bleeding. While unlikely, some adverse events may be permanent.

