An adverse event (AE) is any undesired clinical occurrence in a study subject as indicated by signs, symptoms, illnesses, events that develop or worsen in severity in association with the study when deemed by the Investigator to be related to use of the device or study procedures. The Investigator will document all adverse signs and symptoms regardless of severity or frequency that are either volunteered by subjects or observed during the course of the study that are related to the device. The Investigator will also record adverse experiences of subjects resulting from concurrent illnesses, reactions to concurrent medications, or progression of disease states that the Investigator deems related to the device. Included in the description will be the nature of the sign or symptom, the date of onset, whether the event was serious, the severity, the relationship to study procedures or investigational device, the action taken, the date of resolution, and the outcome. The Principal Investigator will then determine the relationship of the adverse device effect to the investigational device.

Unanticipated Adverse Device Effects

For device studies, part 21 CFR 812.3(s) uses the term unanticipated adverse device effect which is defined as any serious adverse effect on health or safety or any life-threatening problem or death caused by, or associated with, a device, if that effect, problem, or death was not previously identified in nature, severity, or degree of incidence in the investigational plan or application (including a supplementary plan or application), or any other unanticipated serious problem associated with a device that relates to the rights, safety, or welfare of subjects.

An unanticipated adverse effect will be graded as follows:

Mild: Sign or symptom, usually transient, non-life-threatening requiring no special treatment and generally not interfering with usual activities.

Moderate: Sign or symptom, non-life-threatening which may be ameliorated by simple therapeutic measures and may interfere with usual activity.

Major: Sign or symptom that is intense or debilitating but non-life-threatening and that interferes with usual activities. Recovery is usually aided by therapeutic measures and the discontinuation of the study device may be required.

Severe: Any untoward medical occurrence that at any time results in death or life-threatening illness, resulting in persistent or significant disability/incapacity.

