The relationship of the adverse effect to the study is defined as follows:

Probable: An adverse event has a strong temporal relationship to study device, and another etiology is unlikely or significantly less likely.

Possible: An adverse event has a strong temporal relationship to the study device, and an alternative etiology is equally or less likely compared to the potential relationship to study device.

Probably not: An adverse event has little or no temporal relationship to the study device and/or a more likely alternative etiology exists.

Not related: An adverse event has no temporal relationship to study device or has a much more likely alternative etiology.

Reporting Adverse Events (AE) and Serious Adverse Events (SAE)

The Investigator must report all unanticipated adverse device effects that are serious in nature to the clinical study monitor immediately or within twenty-four hours by telephone (see below). If such an unanticipated adverse device effect is reported after normal working hours, the Investigator will leave a voice message at the monitor's telephone number with accompanying report of the unanticipated adverse device effect faxed or sent to the fax number/e-mail address below:

[name], Global VP of Clinical and Regulatory Affairs

Telephone Number (mobile): [contact]

Email: [contact]

A written report prepared by the Principal Investigator must follow within five working days to both the IRB and to Candela and should include a full description of the event and sequence.

MEASURES TAKEN TO PROTECT THE RIGHTS AND WELFARE OF SUBJECTS

Research records will be available to study personnel, and the Institutional Review Board, where applicable. Research records may be used for purposes of medical education, after removal of patient names or other identifying information. Subjects will be required to provide permission for the

 Candela Corporation Confidential	Pilot Study to Evaluate Combined Vbeam[®] Pulsed Dye Laser Treatment and RHOFADÉ™ (oxymetazoline hydrochloride) Topical Cream for Erythematotelangiectatic Rosacea			
	Protocol #	DHF24671	Rev. Date	June 11, 2018

photographs taken of the treatment area during the study to be made available to the investigator and the sponsor for research and marketing purposes, after removal of identifying information. These photographs may be used for lectures, presentations or publications.

RISK/BENEFIT ANALYSIS

Risks

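### The only timed safety report covers serious unanticipated device effects, so serious events in cream-only Arm 2 and purely cream-related serious events in Arm 1 have no stated expedited timeline

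*Combined protocol and SAP*

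**What the plan says.** The section Reporting Adverse Events (AE) and Serious Adverse Events (SAE) contains one rule with a time limit: "The Investigator must report all unanticipated adverse device effects that are serious in nature to the clinical study monitor immediately or within twenty-four hours". This report is made by phone, and a voice message is allowed after hours. The investigator's written report must then follow within five working days, to the IRB and the sponsor.

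The section Unanticipated Adverse Device Effects takes its definition from the device regulation. The effect must be "caused by, or associated with, a device", and the residual limb for other unanticipated serious problems also requires association with a device.

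Two descriptions of an adverse event appear. The opening of Adverse Events (AE) is broad: "any adverse change in health or side effect that occurs in a study participant during their participation in the study". The later, detailed text counts an event "when deemed by the Investigator to be related to use of the device or study procedures". Among the items to record is "the relationship to study procedures or investigational device". The causality scale has four categories, each worded against the study device; Probable, for example, reads "An adverse event has a strong temporal relationship to study device, and another etiology is unlikely or significantly less likely".

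The synopsis makes adverse events a safety endpoint in both arms, and Table 2 schedules adverse events and serious adverse events at every visit. The cream is described under Study Drug, separately from Study Device.

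**The concern.** The section is headed for adverse events and serious adverse events in general, yet its timed duty was written for a device trial. This trial has two study treatments. All subjects, up to 60, use the cream, and Arm 2 uses nothing else. A site that follows the section exactly has no stated duty to expedite a serious event caused by the cream.

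At stake is how soon the sponsor and IRB would hear of such an event while other subjects at two sites keep applying the product daily. The protocol itself lists warnings for the cream, including blood-pressure effects and acute narrow-angle glaucoma. The sponsor may withdraw a subject to protect health and may stop the study after an interim look; both powers work only as fast as the information arrives.

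There is also an ascertainment question. If one site records under the broad definition and the other under the narrow one, the both-arms adverse event endpoint is not collected on the same footing.

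**Working it through.** No arithmetic applies, and the plan gives no figure to reproduce. The check is to read the rule against each kind of serious event.

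1. **Scope of the clock.** The 24-hour duty covers serious unanticipated adverse device effects. The five-working-day report is written to follow that call, so it has the same scope. The after-hours sentence also refers to such a device effect.
2. **Need for a device.** Both limbs of the definition require association with a device.
3. **Who has device exposure.** Study Design states that Arm 2 gets no laser, and the optional test spots are for Arm 1 only.

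| Serious event | Timed report stated? | Reason |
|---|---|---|
| Arm 1, laser, unanticipated | Yes | Inside the rule |
| Arm 1, laser and cream hard to separate | Depends on attribution | Being associated with a device may be enough |
| Arm 1, purely cream | No | No device association |
| Arm 2, any cause | No | No laser given |
| Arm 1, laser, fully anticipated | No | Excluded by the word unanticipated |

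The last row is the smallest group. Anticipated Adverse Effects lists the known laser effects and adds "While unlikely, some adverse events may be permanent", but an effect whose severity or incidence was not identified beforehand still counts as unanticipated.

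4. **Other routes.** Under Protocol Revisions and/or Deviations, when emergency medical procedures are used, "all such procedures must be promptly reported to the sponsor and the IRB/IEC". That covers the procedure, sets no number of hours or days, and does not reach a serious event that needed no emergency procedure. Regular phone and e-mail contact and monitoring visits are planned, again with no time limit for a serious event. No other timeline for serious events appears in the document.
5. **Definition and causality.** The narrow definition reaches the device and study procedures. Two sentences that tell the investigator what to document are narrower still and mention only the device. Both fall short of the broad definition and of the both-arms endpoint. In the four causality categories, the cream can enter only as an alternative etiology, which moves a cream reaction toward the two unrelated categories. In Arm 1 the cream is applied in the office straight after the laser, so attribution is likely to be uncertain where it matters most.

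**The case against.** The strongest reply is that the gap is one of wording. The study is to be conducted in compliance with sponsor SOPs, 21 CFR and GCP, and Quality Assurance and Study Monitoring requires data to be reported in line with them. Those commitments bind the sites and may contain a deadline for serious events. This stands as a limit on the consequence. It does not repair the section: the sponsor wrote out the device deadline there, and a site reading it finds no other deadline and no pointer to one.

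The cream is also approved and used for its labelled indication. Its common reactions are listed at 1–2% through four weeks and 2–3% over a year. Vascular disease, scleroderma and cardiac disorders are exclusions. Narrow-angle glaucoma is not named, but exclusion 21 lets the investigator exclude any condition that makes participation unsafe, and a subject can be withdrawn at any time to protect health. All of this stands and keeps the point modest.

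Three stronger readings are tempting, and the documents do not support them.

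- A reader might infer that serious events in Arm 2 go uncollected. They are an endpoint in both arms and are scheduled at every visit; what is missing is the expedited report.
- A reader might infer that relationship to the cream cannot be recorded at all. The recorded items include relationship to study procedures, and the protocol lists dispensing and applying the cream among its procedures, so a cream reaction could be entered there. What is absent is a separate rating for the cream.
- A reader might infer a predicted delay from the small minimum number of monitoring visits. More visits and regular contact are allowed, so that number does not measure reporting time.

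**Conclusion.** The point holds as a matter of scope. As written, the 24-hour and five-working-day reports do not reach any serious event in Arm 2 or a purely cream-related serious event in Arm 1. The narrow recording text and the device-only causality categories fit poorly with the broad definition and the both-arms endpoint.

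Its size is a contrast in the text: a 24-hour limit for one class of serious event and no stated limit for the other. The documents give no serious-event rate for either treatment, so no number of late reports and no length of delay is claimed. No efficacy comparison is affected.

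Confidence is high on what the reporting section says and lower on the practical consequence, because the SOPs are not available and may already set a deadline. The conclusion assumes that the cream is not a device, which is how the protocol presents it. The correction is worth making because it is cheap and bears on subject safety.

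**What to change.** 1. Replace the timed rule with one covering both treatments, for example: *Any serious adverse event in either arm, anticipated or not and whatever its suspected cause, is to be telephoned to the study monitor at once and at the latest within 24 hours.* Keep the written report to the IRB and sponsor within five working days. Reword the after-hours sentence to match. Unanticipated device effects remain a subset, so the existing duty is not weakened.
2. Define serious. The protocol lists SAE as an abbreviation but gives no definition. At a minimum, include the outcomes already named under the Severe grade (death, life-threatening illness, persistent or significant disability), plus any others the SOPs require. If the SOPs already set a deadline, cite it in this section.
3. Use the broad adverse event definition for recording in both arms, in place of the narrower definition and the device-only recording sentences.
4. Add a second causality rating, for relationship to the cream, using the same four categories, and list it among the recorded items.

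The cost is wording changes, one added item on the adverse event form and notice to the IRB, with no new visit, test or committee. The downside is some extra expedited reports, including a few for anticipated or unrelated events. Their number cannot be estimated from the documents but should be small with at most 60 subjects.
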